# 6.3.6. COVID-19 Related Endpoint 2 – Proportion of CAP patients who experienced severe clinical outcome(s) between patients with or without COVID-19 coinfection with Sp

These analyses will assess differences in the severe clinical outcomes between patients with or without laboratory-confirmed COVID-19 coinfection with *Sp* identified by any means (e.g., UAD, Binax, and bacterial culture) and separately by penumococcal carriage.

#### 6.3.6.1. COVID-19 Related Endpoint 2 - Main Analysis

The patients with COVID-19 will be divided into two groups:

- those with coinfection with Sp identified by any means (e.g., UAD, Binax, bacterial culture)
- Those without coinfection with Sp identified by any means (e.g., UAD, Binax, bacterial culture)

The severe clinical outcomes are:

- Admitted to ICU (yes vs. no)
- PaO2/FiO2 ratio <250 mmHg (yes vs. no)

DMB02-GSOP-RF02 5.0 Statistical Analysis Plan Template 05-Dec-2019
PFIZER CONFIDENTIAL
Page 39
TMF Doc ID: 98.03

- Respiratory rate >30 breaths/min (yes vs. no)
- Died (yes vs. no)
- Received mechanical ventilation (yes vs. no)
- Diagnosed as ARDS (yes vs. no)
- Any one of the above (yes. vs. no)

The difference in the severe clinical outcomes between the two groups will be evaluated using Chi-square or Fisher's Exact test, as appropriate.

The analysis will also be done stratifying by age group (60-74 years,75-84 years and ≥85 years), sex, and pneumococcal risk status.

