- c. If subject readmitted within 14 days of the qualifying hospitalisation, that follow up hospitalisation will be considered part of the same event as the initial hospitalisation. An additional urine sample will be taken upon readmission.
- d. Any additional results from standard of care pneumococcal and viral respiratory testing, including COVID-19 and RSV, not captured during Visit 1 Day 1 could be recorded at Visit 2 Day 30 (and data can be entered on Visit 1 eCRF).
- e. Any additional information on hospitalisation data electronic case report form (eCRF) items not captured during Visit 1 Day 1 could be recorded at Visit 2 Day 30.
- f. Please see full details of which adverse events to record in Section 16 Table 8.
- g. Information to calculate Charlson Comorbidity Index (CCI) will be collected. Diagnosis codes such as International Classification of Diseases (ICD) discharge codes may be provided as a separate file linked by participant number to calculate CCI or data will be collected via eCRF at Day180 or prior visit.
- h. SOC assessments (for example, details of current illness, vital signs, radiology exams, microbiological testing and others) could be performed before hospital admission or enrolment (Date of Visit) and captured in eCRF.

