11.2. Biological Samples 11.2.1. Blood and Respiratory Samples

All blood and respiratory specimens collected as part of SOC for culture (eg, blood, pleural fluid, transtracheal aspirate, bronchoalveolar lavage or other respiratory tract specimen) will undergo bacterial culture at the local site laboratory for the identification of SP according to their standard methodology. Best practices for blood culture collection involved obtaining 2 sets of blood cultures before antibiotic administration if possible. The blood culture should be collected and timed according to the local institution's policy using different sampling sites. Anaerobic and aerobic samples should be collected.

Whenever possible, blood should be collected from peripheral veins. Results of blood cultures (including antibiotic susceptibility) from this SOC bacterial culture testing will be recorded in the eCRF.

For sputum specimens collected as part of standard –of care testing, specimen quality will be assessed using the specimen's standard –of care Gram stain results. Only bacterial culture results from high-quality sputum specimens will be use in case categorisation for the VE analysis, but all pneumococcal isolates will be serotyped regarding of specimen quality.

Serotyping, Antimicrobial Resistance and Molecular Biology Testing of the Isolates

Pneumococcal bacterial isolates from SOC specimens will be shipped and analyzed in the Pneumococcal Reference Laboratory from the Centro Nacional de Microbiología which belongs to the Instituto de Salud Carlos III (ISCIII). In no case will there be any interference with the autonomous regional pneumococci monitoring systems at the sites participating in the study.

The ISCIII reference laboratories provide data and information of sanitary interest on the microorganisms that cause infectious diseases, environmental pollutants situation and the development of new technologies and/or surveillance strategies and control in accordance with the priorities established by the Ministerio de Sanidad, Consumo y Bienestar Social (MSCBS) following the recommendations of the European Centre for Disease Prevention and Control (ECDC). The pneumococcal reference laboratory is located in Majadahonda which is a city in Madrid region, it carries out a passive surveillance and receive the isolates from hospitals of all the Spanish regions.

Identification and Serotyping

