#### Results of Culture and Urine Assays for S. pneumoniae

Sp+ is defined as the identification of Streptococcus pneumoniae via any of the following three diagnostic methods:

Microbiology culture: As part of standard of care, all blood and respiratory specimens (e.g., blood, pleural fluid, transtracheal aspirate, bronchoalveolar lavage or other respiratory tract specimen) will undergo bacterial culture at the local site laboratory for the identification of S. pneumoniae according to their standard methodology. Results of blood cultures (including antibiotic susceptibility) from this standard of care bacterial culture testing will be recorded in the CRF.

DMB02-GSOP-RF02 5.0 Statistical Analysis Plan Template 05-Dec-2019
PFIZER CONFIDENTIAL
Page 21
TMF Doc ID: 98.03

For sputum specimens collected as part of SOC testing, specimen quality will be assessed using the specimen's standard-of-care Gram stain results. Only bacterial culture results from high-quality sputum specimens will be used in case of categorization for the VE analysis. However, all pneumococcal isolates will be serotyped regardless of specimen quality.

Pneumococcal bacterial isolates from standard of care specimens will be shipped and analyzed in the Pneumococcal Reference Laboratory from the Centro Nacional de Microbiología of the Instituto de Salud Carlos III (ISCIII). The following antimicrobials will be evaluated: penicillin, amoxicillin, cefotaxime, erythromycin, clindamycin, tetracycline, and levofloxacin.

- Binax assay: If a positive result is issued from the urine testing, when analysed by the Pfizer VRD laboratory, then it is considered Sp+. This assay does not provide Sp serotype information.
- UAD assay: The UAD-1 detects 13 serotypes (1, 3, 4, 5, 6A, 6B, 7F, 9V, 14, 18C, 19A, 19F, 23F) used in Pfizer's 13vPnC vaccine. The UAD-2 assay, using the same Luminex xMAP bead technology, detects 11 additional serotypes (2, 8, 9N, 10A, 11A, 12F, 15B, 17F, 20, 22F, 33F). A maximum of two serotypes can be reported from each one of the UADs.

Any participant who is not determined as Sp+ by any of the three diagnostic methods will be considered as Sp-, unless they have missing results from all three diagnostic methods. If any culture identified Sp+, antibiotic susceptibility will be assessed at the local laboratory and results are to be entered in the CRF.

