## 4.8.5. Sp+ Subpopulation

This subpopulation is composed of the per-protocol population that are also Sp+ by any of the following three diagnostic methods:

- microbiology culture results of S. pneumoniae as a pathogen from local lab entered in the eCRF; or
- 'POS' results from Binax assay; or
- 'POS' results from UAD assay for any of the 24 serotypes.

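### COVID-19 Related Endpoint 2: co-infection counts clinician-ordered cultures with no specimen-date window, so its association with severe outcomes may be biased by who is cultured and when

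*SAP*

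**What the plan says.** **Exposure.** SAP 6.3.6.1 splits COVID-19 patients into "those with coinfection with Sp identified by any means" (UAD, Binax or bacterial culture are given as examples) and those without. SAP 3.3.2 and Protocol Section 8 define the endpoint in the same way.

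**Cultures.** Protocol 11.2.1 covers "All blood and respiratory specimens collected as part of SOC for culture", including "transtracheal aspirate, bronchoalveolar lavage or other respiratory tract specimen". These are ordered by clinicians and not required by the study. The culture arm of the Sp+ definition in SAP 4.8.5 is "microbiology culture results of S. pneumoniae as a pathogen from local lab entered in the eCRF". No collection-date limit appears there, in SAP 3.4 or in SAP 6.3.6.1. The high-quality sputum rule in SAP 3.4 is stated for the VE analysis only.

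**Late entry.** Footnote d of the Schedule of Activities (Protocol Section 6) covers "Any additional results from standard of care pneumococcal and viral respiratory testing"; results "not captured during Visit 1 Day 1 could be recorded at Visit 2 Day 30".

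**Patients not cultured.** SAP 3.4 states: "Any participant who is not determined as Sp+ by any of the three diagnostic methods will be considered as Sp"-negative, unless results from all three methods are missing.

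**Urine.** Protocol 9.1 has BinaxNOW and UAD1/2 run on study urine from every enrolled participant, nominally at Visit 1.

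**Outcomes and test.** The outcomes are ICU admission, PaO2/FiO2 below 250 mmHg, respiratory rate above 30, death, mechanical ventilation, ARDS, and any of these. The groups are compared by chi-square or Fisher's exact test, overall and stratified by age group, sex and pneumococcal risk status.

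**The concern.** The exposure has two parts. Urine testing is the same for everyone. Culture depends on a clinical decision, and nothing in the definition ties that decision to the time of admission. ICU admission, ventilation and ARDS accrue during the stay, so they can come before a culture and be the reason for it. Two problems follow.

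- **Differential ascertainment.** If one severity group is cultured more, more of its pneumococci are found, while patients who were never cultured are coded as negative.
- **Reverse timing.** A pneumococcus isolated from a specimen taken after intubation can be counted as co-infection, although the outcome came first.

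The objective is to learn whether severe outcomes differ with co-infection. As written, a difference could not be separated from a difference in testing.

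The outcomes are not all exposed to the same degree. Protocol 10.3 collects respiratory rate as an initial value, so a later culture cannot have preceded it, although differential culturing can still act. Early death shortens the time in which a culture could be taken.

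**Working it through.** The documents give no sample size, event count or error rate for this comparison, so there is no planned figure to reproduce. They also give no culture frequency, timing or yield by severity. **Every rate below is an assumption.** The calculation asks what odds ratio would appear if co-infection and severity were truly unrelated.

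**Inputs**
- p: true pneumococcal prevalence, 5%, 10% or 20%, equal in both severity groups
- s: sensitivity of study urine, 60%, 75% or 90%, equal in both groups
- q: share of patients cultured, set separately for severe and non-severe
- c: sensitivity of culture in infections that urine missed, 30%
- h: late or non-causal pneumococcal yield per cultured patient without true infection, 0 to 5%

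**Formula**

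P(labelled co-infected) = p[s + (1 − s)qc] + (1 − p)qh

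Spurious OR = odds of the label in severe patients ÷ odds in non-severe patients.

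**Worked case** (p = 10%, s = 75%; severe 90% cultured with h = 2%; non-severe 50% cultured with h = 0)
- Severe: 0.10 × (0.75 + 0.25 × 0.9 × 0.3) + 0.90 × 0.9 × 0.02 = 0.08175 + 0.0162 = 0.09795
- Non-severe: 0.10 × (0.75 + 0.25 × 0.5 × 0.3) = 0.07875
- OR = (0.09795/0.90205) ÷ (0.07875/0.92125) = 1.27

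**Results over the assumed ranges**

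| Scenario | Spurious OR |
|---|---|
| Severe 90% vs non-severe 40% or 60% cultured, h = 0 | 1.01–1.11 |
| Same, h = 1–2% in both groups | 1.03–1.33 |
| 90% vs 50% cultured, s = 75%, h = 1–5% in severe only, p = 20% | 1.10–1.33 |
| Same, p = 10% | 1.15–1.63 |
| Same, p = 5% | 1.27–2.23 |
| Equal culturing (90% in both), same h in both | 1.00 |
| Severe cultured less (60% vs 90%), h = 0–2% | 0.85–0.99 |
| Urine only (no culture in the definition) | 1.00 |

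**A simpler model as a cross-check.** Let u be the share positive by urine (8–12% in both groups), q the share cultured (80% vs 30%, or 90% vs 40%) and y the yield among cultured urine-negatives (3–6%). Then P = u + (1 − u)qy.
- Low end, u = 0.12, y = 0.03, 90% vs 40%: 0.14376 vs 0.13056, OR 1.12
- High end, u = 0.08, y = 0.06, 80% vs 30%: 0.12416 vs 0.09656, OR 1.33

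**Reading.** The bias is small where culture only adds infections that urine missed. It becomes material where late yield is concentrated in severe patients and prevalence is low. It reverses if severe patients are cultured less. The urine-only value of 1.00 depends on equal urine sensitivity and timing. Timing is not assured: footnote a of the Schedule of Activities allows later enrolment when a patient cannot consent, with intubation as its example.

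**The case against.** The strongest reply is that no passage shows severe patients being cultured more or later. A reader might infer that the association is inflated. The documents do not support that as a fact, because direction and size depend on rates they do not give.

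A reader might also infer a rule that any specimen from any day of the stay counts. There is no such rule. Footnote d concerns data entry, and some text points to early sampling: Protocol 11.2.1 describes blood cultures before antibiotics, and footnote h allows standard-of-care tests done before admission or enrolment. SAP 4.8.5 also requires the isolate to be recorded as a pathogen, which should remove some colonising strains, though not a genuine late infection. What remains is that no window is set. By contrast, SAP 3.4 ties standard-of-care viral results to specimens collected on admission, and eligibility uses 48 hours.

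The following also stand on the other side:
- Study urine from all enrolled participants makes a large part of ascertainment independent of severity. This limits the bias without removing it.
- Age, sex and risk status are already handled by stratification. Regression on them is not needed here and would not remove detection bias.
- The any-means wording is the protocol's own, and the analysis goes ahead only if COVID-19 is frequent enough (Protocol 12.4.3).

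The separate analysis by saliva carriage (SAP 6.3.6) does not answer the point, because carriage is not infection. The UAD and Binax subpopulations (SAP 4.8.1 and 4.8.2) are defined but not used for this endpoint.

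**Conclusion.** The point holds as a risk of bias in one exploratory comparison. Co-infection has no sampling window, depends partly on clinician-ordered cultures, and codes uncultured patients as negative, while several outcomes can precede and prompt the culture. The association may be biased upward if severe patients are cultured more or later, and downward if they are cultured less.

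Under assumed rates and no true association, the spurious odds ratio is about 1.0 to 1.3 when severe patients are cultured more. It reaches 2.23 in the most extreme late-yield case (p = 5%, 5% late yield in severe patients only) and lies between 0.85 and 0.99 when they are cultured less. These figures show scale and do not estimate what this study will produce.

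The point does not extend to COVID-19 Related Endpoint 1, which compares COVID-positive with COVID-negative patients; nothing shown here supports changing that definition. The primary VE analysis is unaffected.

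**What to change.** For COVID-19 Related Endpoint 2 only, amend SAP 3.3.2 and 6.3.6.1 as follows.

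1. **Main definition.** Define co-infection from the Visit 1 study urine (valid UAD-1/2 or Binax) plus cultures from specimens collected within 48 hours of admission, where the specimen date is available. The window limits reverse timing.
2. **Urine-only analysis.** Report it beside the main one. Early culturing can still differ by severity, and this analysis takes culture out of the definition.
3. **Any-means definition.** Keep it as a sensitivity analysis.
4. **Tabulate by severity** the share cultured, the time from admission to culture, and the time from admission to urine collection. The last is needed because intubated patients may be enrolled late, so urine timing may also differ.

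**Cost.** This is SAP wording and uses data already collected. A few late or culture-only positives leave the main definition, with a small loss of sensitivity. The culture fields listed in SAP 3.4 do not name a collection date, so its availability should be confirmed first.

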- To estimate incidence rates for hospitalised CAP among adults aged ≥60 years with underlying at-risk and high-risk medical conditions, in aggregate and for individual risk conditions within the limitations of the expected under ascertainment of hospital-based screening process and current diagnostic testing.

Additional 2019 Novel Coronavirus Disease 2019 (COVID-19)-related Exploratory Objectives

- To determine if the frequency of pneumococcal infection differs between hospitalised CAP patients with COVID-19 infection compared to those without COVID-19 infection, overall and stratified by age, sex, and pneumococcal risk status.
- Among the subset of hospitalised CAP patients with COVID-19 identified, to determine if the proportion who experience severe clinical outcomes (eg, intensive care unit [ICU] stay, mechanical ventilation, prolonged hospitalisation, and sequelae) differs between those with pneumococcal co-infection compared to those without pneumococcal co-infection, overall and stratified by age, sex, and pneumococcal risk status.
- Using a test-negative design to determine the VE of PCV13 against severe COVID-19 clinical outcomes among COVID-19 positive hospitalised CAP patients, overall and among immunocompetent persons only.
- To assess if pneumococcal carriage differs for those with current or past COVID-19 infection, overall and stratified by age, sex, and pneumococcal risk status.

Additional 2022 Respiratory Syncytial Virus (RSV) Exploratory Objective

• To determine the proportion of persons with RSV infection among adults 60 years of age and older presenting with CAP by testing saliva specimens using the PCR method.

Study design

This study is a low interventional, prospective, multicentre, hospital-based study involving adults 60 years of age and older hospitalised with CAP at participating sites. Hospital surveillance data will be used for incidence rates calculations. Vaccine effectiveness will be calculated using a TND. The approximate study duration will be 4 years.

Population

This study will prospectively enroll adults, aged 60 years and over, who are hospitalised with CAP in one of the study hospitals: Hospital Universitario de Móstoles, Hospital Universitario Fundación de Alcorcón, and Hospital Rey Juan Carlos de Móstoles (as of February 2022, additional sites may be included at a later date).

Variables

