12.4.1. Vaccine Effectiveness

If either PCV13 or PPV23 coverage is <10% or >90%, we will assess whether valid VE estimates can be generated for the involved vaccine. If appropriate, we will proceed as follows; odds ratio of having received PCV13 and PPV23 for cases and controls with 95% CI for odds ratio will be calculated. See details on case and control assignment in Section 12.1.1. We will calculate VE as 1-OR x 100. In addition to constructing crude OR and VE estimates, we will perform unconditional logistic regression modelling to assess VE after adjustment for potentially confounding factors. Because of the risk-based approach to catch up vaccination in the over 60 cohort, we will also perform a second adjusted analysis, selecting non-vaccine-type controls similar the VT-serotype cases based on propensity score matching. Further, we will use a two-sided alpha of .025 for all analyses if final VE analysis is not conducted at the interim analysis. If interim analysis is final VE analysis, a two-sided alpha of .05 will be used in the final tables. A second model will be developed excluding immunocompromised persons to evaluate VE without those that may not be able to respond to the vaccine. Only adjusted estimates will be considered the final VE. Time from vaccination will be accounted for in the adjusted analyses. The comparison of the estimates of the effectiveness between PCV13 and PPV23 will be performed using the z-score test. The null hypothesis will be that there is no difference between the two estimates.

For the other study objectives, descriptive analysis will be carried out, presenting the absolute and relative frequencies of the qualitative variables and main measures of centralisation and dispersion in case of quantitative variables. Comparisons between proportions will be performed using χ^2 test, the Fisher's exact test, or the Likelihood Ratio test, as appropriate. For quantitative variables, the Student's t-test or the Analysis Of Variance (ANOVA) test will be used, and when data did not show normality in the Kolmogorov-Smirnov test, the Kruskal-Wallis and Mann-Whitney tests will be used.

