12.4.3. Additional COVID-19 and RSV Exploratory Analyses

Additional statistical methods and data analysis for the COVID-19 and RSV exploratory analyses will be described in the SAP. These analyses will be undertaken if COVID-19 continues to occur at a sufficient frequency during enrolment in the surveillance region to allow for a meaningful analysis.

PFIZER CONFIDENTIAL CT45-GSOP-RF152.0 Low-Interventional Study Protocol Template 05-Dec-2019 Page 56 of 70

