# 6.3.5.1. COVID-19 Related Endpoint 1 - Main Analysis

The following calculations will be made for overall and stratified by age group, sex, and pneumococcal risk status among COVID-19 subpopulations (test positive or negative), i.e., all enrolled population with a valid results from COVID-19 viral testing. The following calculations will be made:

- Proportion (95% CI for proportion) of CAP events with pneumococcus among COVID-19 test positive cases
- Proportion (95% CI for proportion) of CAP events with pneumococcus among COVID-19 test negative cases

These will also be calculated for the following subgroups: age group (60-74 years, 75-84 years and ≥85 years), sex, and pneumococcal risk status.

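### COVID-19 Endpoint 2 compares severe outcomes by pneumococcal co-infection with a crude test only and plans no overall estimate adjusted for age, sex or risk status

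*SAP*

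**What the plan says.** The protocol's exploratory COVID-19 objective is "to determine if the proportion who experience severe clinical outcomes" "differs between those with pneumococcal co-infection compared to those without pneumococcal co-infection, overall and stratified by age, sex, and pneumococcal risk status". For methods, Protocol 12.4.3 refers onward: "Additional statistical methods and data analysis for the COVID-19 and RSV exploratory analyses will be described in the SAP".

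SAP 6.3.6.1 forms two groups of COVID-19 patients, with and without pneumococcus identified by any means. It lists six severe outcomes (ICU admission, PaO2/FiO2 below 250 mmHg, respiratory rate above 30, death, mechanical ventilation, ARDS) and a seventh indicator for any of them. The comparison is then specified: "The difference in the severe clinical outcomes between the two groups will be evaluated using Chi-square or Fisher's Exact test, as appropriate". One further sentence follows: "The analysis will also be done stratifying by age group (60-74 years,75-84 years and ≥85 years), sex, and pneumococcal risk status".

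No regression, Mantel-Haenszel or other pooled estimate, matching, or effect measure with a confidence interval is named for this endpoint.

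**The concern.** Co-infection is not assigned at random. Age and comorbidity may affect both the chance of a severe outcome and the chance that pneumococcus is found. If they do, the crude comparison mixes their effect with any association of co-infection itself, and it can show a difference that is not there or hide one that is.

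The stratified repeats help within each stratum, but they do not produce one adjusted overall answer, and the objective asks for an overall answer as well as a stratified one. If the three factors are taken separately, which is the likely reading although the SAP does not say so, each table also leaves the other two factors uncontrolled.

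At stake is how an exploratory finding would be reported. A crude difference in death or ICU admission by co-infection status is easily read as a property of co-infection.

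**Working it through.** **Comparison within the SAP.** There is no stated sample size, event rate or expected effect for this endpoint, so there is no figure to reproduce. The useful check is against the next endpoint.

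| | COVID-19 Endpoint 2 (SAP 6.3.6.1) | COVID-19 Endpoint 3 (SAP 3.3.2, 6.3.7.1) |
|---|---|---|
| Patients | COVID-19-positive CAP | COVID-19-positive CAP |
| Outcomes | Six severe outcomes plus any | The same |
| Exposure | Pneumococcal co-infection, not randomised | PCV13 receipt, not randomised |
| Overall analysis | Chi-square or Fisher's exact test | Propensity-score matching, then conditional logistic regression |
| Age, sex, risk level | Strata only | In the matching score (list in SAP 6.1.1.2) |
| Effect measure | None named | OR, reported as VE |

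The covariates are therefore already collected and coded, and the SAP already adjusts for them when it models these outcomes.

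**Illustration 1: age only, no true effect.** All inputs are assumptions; the documents give none of them. The three age bands are the SAP's (60-74, 75-84, 85 and over). The age mix of patients without co-infection is set at 45/33/22%. Severe risk depends on age alone, so the true OR is 1.00 in every band.

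Crude risk in a group = sum over bands of (share of band × risk in band). Crude OR = [p1/(1−p1)] / [p0/(1−p0)], where p1 is the risk with co-infection and p0 the risk without.

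- Co-infected much older (20/35/45%), risks 15/30/50%: p1 = 0.20×0.15 + 0.35×0.30 + 0.45×0.50 = 0.360; p0 = 0.45×0.15 + 0.33×0.30 + 0.22×0.50 = 0.2765; OR = 0.5625/0.3822 = **1.47**.
- Co-infected younger (60/28/12%), same risks: p1 = 0.090 + 0.084 + 0.060 = 0.234; OR = 0.3055/0.3822 = **0.80**.
- Moderate shift (30/35/35%), risks 20/30/40%: p1 = 0.305; p0 = 0.277; OR = **1.15**.
- Same age mix in both groups, or risk flat by age: OR = **1.00**.

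With 10% co-infected and a two-sided 5% test (normal approximation), the chance that the crude test rejects when there is no effect is:

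| Scenario | Crude OR | 500 patients | 1,000 patients |
|---|---|---|---|
| Much older | 1.47 | 25% | 42% |
| Younger | 0.80 | 9% | 14% |
| Moderate shift | 1.15 | 8% | 10% |
| Same mix | 1.00 | 5% | 5% |

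An age-stratified pooled OR has expectation close to 1.00 in all of these, because the stratum ORs are all 1.00.

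**Illustration 2: age and high-risk status, no true effect.** Assumed: age shares 45/35/20%; high risk 30/36/42% by age; severe risk 20/35/55% by age, with OR 1.5 for high risk. If co-infection is 5/8/12% by age and 1.5 times that in high-risk patients, p1 = 0.414 and p0 = 0.347, so the crude OR is 1.33. With milder gradients (7/8/9%, 1.1 times) p1 = 0.369 and p0 = 0.351, and the crude OR is 1.08.

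The result therefore depends on how strongly age and risk are tied to co-infection, and the plan does not give this.

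**The case against.** The strongest reply is that the SAP delivers the endpoint the protocol defined: percentages compared overall and stratified by these three factors. Where the sponsor wanted adjustment, it said so, as in Endpoint 3. Protocol 12.4.1 also sets the tone: "For the other study objectives, descriptive analysis will be carried out", with chi-square and Fisher's tests named for proportions. The COVID-19 analyses are conditional on COVID-19 being frequent enough, and SAP 5.1 disclaims hypothesis tests and decision rules for the study. All of this stands. It makes the point minor and means that there is no departure from the protocol. It does not supply an adjusted overall estimate, and SAP 5.1 does not change the fact that SAP 6.3.6.1 plans significance tests to evaluate the difference.

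Four stronger readings are tempting and are not supported:

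- *The comparison is confounded.* No document gives age, sex or risk status by co-infection status. Confounding is a risk here, not a finding.
- *The endpoint judges whether co-infection makes COVID-19 worse.* The objective asks only whether proportions differ.
- *The crude test will lose power to detect a real effect.* That depends wholly on chosen inputs, and attenuation of an OR is not all confounding. Under the second set of assumptions with a true OR of 2, making co-infection fall with age (12/8/5%, 0.8 times in high-risk patients) gives a crude OR of 1.51. Co-infection flat at 8%, with no confounding at all, already gives 1.87, because odds ratios are non-collapsible.
- *COVID-19 Endpoint 1 has the same fault.* SAP 6.3.5.1 plans proportions with 95% CIs and no test: "These will also be calculated for the following subgroups: age group". How often pneumococcus is found by COVID-19 status is a descriptive quantity, and crude proportions answer it.

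**Conclusion.** The gap is real and minor. For COVID-19 Endpoint 2 the only overall comparison is unadjusted, and the strata are not combined, so the overall answer is open to confounding by age, sex and risk status. The adjacent endpoint on the same outcomes is adjusted.

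The size and sign of any bias cannot be obtained from the documents. On the assumptions shown, with no true effect, the crude OR lies between about 0.8 and 1.5. It is close to 1.1 with mild gradients and exactly 1.0 when the age and risk mix is equal. These figures show what is possible and do not predict the result. The conclusion itself rests only on the text: two non-randomised groups, a crude test and no pooled estimate.

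**What to change.** In SAP 6.3.6.1, add for each severe outcome an OR with 95% CI for co-infection, adjusted for age, sex and risk level. Use logistic regression, or a Mantel-Haenszel analysis over the strata already defined. State that the overall interpretation rests on this estimate. Keep the chi-square or Fisher's test and the stratified tables as descriptive companions, and say whether the strata are separate or joint.

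State in advance what happens when an outcome is rare. Co-infection, continuous age, sex and a three-level risk factor use 1 + 1 + 1 + 2 = 5 model terms. If the 10-events-per-covariate rule in SAP Appendix 3.3 were applied to all of them, that is 5 × 10 = 50 events. Outcomes with fewer, possibly death or ARDS, need Firth penalisation or a shorter covariate list.

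The cost is a paragraph of SAP text and a few models on data already collected. The drawback is that for rare outcomes the adjustment will be limited and the intervals wide. If the sponsor prefers not to add the model, the least change is to label the crude comparison as descriptive and not to be read as an association independent of age, sex and risk.
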